### **2.4.1 Risks of receipt of RTS,S/AS01E or tetanus toxoid or tetanus/diphtheria vaccine**

Recipients of the investigational vaccine (RTS,S/AS01E) may experience pain and/or swelling at the injection site, fever, headache, fatigue, nausea, vomiting and/or abdominal pain, joint pain and/or muscle aches but these features are usually only mild. About 1:1,000 children have been reported to develop a febrile convulsion after receipt of RTS,S/AS01E. In the first three years of RTS,S/AS01E plus SMC trial only five children have experienced a febrile convulsion and it is not known if all these children had received RTS,S/AS01E. In the large Phase III study, MALARIA-055, an imbalance in meningitis cases of any etiology (i.e. including cases with confirmed etiology and cases with no etiology found), with no cluster in time-to-onset, was observed in children 5-17 months of age at first dose [3]. Potential immune-mediated disease (pIMD) is a theoretical concern with adjuvanted vaccines but no evidence of autoimmune disease caused by RTS,S/AS01 has been observed. Nonetheless, both meningitis and pIMDs will be monitored as AEs of specific interest for the duration of the study.

Vaccination with tetanus or tetanus/diphtheria toxoids may cause mild local and systemic reactions and anaphylaxis has been recorded as a very rare adverse event following administration of this vaccine. Some children in the extension study will receive five doses of tetanus or tetanus/diphtheria toxoids during their first five years of life. Administration of a fourth dose of tetanus or tetanus/diphtheria/pertussis vaccine at the age of approximately 18 months is recommended in some routine infant immunization programmes. There is less experience of administration of a fifth dose. However, tetanus toxoid is recommended at each pregnancy in low income countries and many women must have received at least five doses of tetanus toxoid without any reports of adverse events.

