##### A.2 Definition of Adverse Events of Special Interest

AEs of specific interest for safety monitoring include all seizures occurring within 30 days post-vaccination, meningitis and pIMDs and will be recorded in the CRF.

Meningitis cases: For the further evaluation of the safety signal of meningitis in the investigational vaccine groups all cases of meningitis occurring during the study will be reported as a SAE.

pIMDs are a subset of AEs that include autoimmune diseases and other inflammatory and/or neurologic disorders of interest which may or may not have an autoimmune etiology. AEs that need to be recorded and reported as pIMDs include those listed in Table A.

Table A. List of Potential Immune-mediated Diseases:

| Neuroinflammatory disorders  | Musculoskeletal disorders  | Skin disorders  |
|--|--|---|
| 
 
• Cranial nerve disorders, including paralyses/paresis (e.g. Bell's palsy)
 
• Optic neuritis
 
• Multiple sclerosis
 
• Transverse myelitis
 
• Guillain-Barré syndrome, including Miller Fisher syndrome and other variants
 
• Acute disseminated encephalomyelitis, including site specific variants: e.g. non-infectious encephalitis, encephalomyelitis, myelitis, myeloradiculoneuritis
 
• Myasthenia gravis, including Lambert-Eaton myasthenic syndrome
 
• Immune-mediated peripheral neuropathies and plexopathies,
 
 | 
 
• Systemic lupus erythematosus and associated conditions
 
• Systemic scleroderma (Systemic sclerosis), including diffuse systemic form and CREST syndrome
 
• Idiopathic inflammatory myopathies, including dermatomyositis
 
• Polymyositis
 
• Antisynthetase syndrome
 
• Rheumatoid arthritis, and associated conditions including juvenile chronic arthritis and Still's disease
 
• Polymyalgia rheumatica
 
• Spondyloarthritis, including ankylosing spondylitis, reactive arthritis (Reiter's
 
 | 
 
• Psoriasis
 
• Vitiligo
 
• Erythema nodosum
 
• Autoimmune bullous skin diseases (including pemphigus, pemphigoid and dermatitis herpetiformis)
 
• Alopecia areata
 
• Lichen planus
 
• Sweet's syndrome
 
• Localised Scleroderma (Morphea)
 
 |

|  |  |  |
|--|--|--|

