#### D. Reporting of adverse events and SAEs

All serious adverse events will be reported using a SAE report form which will have a detailed narrative of the events including information on the date the event started, severity, possible relationship to study drugs, concomitant medications, action taken, and outcome of the event.

A list of all SAEs will be compiled monthly or three monthly as requested by the DSMB and provided to the DSMB and GSK. Any SAE potentially related to the vaccine or drug administration will be reported to the DSMB and institutional Ethics Committees within 72 hour.

SAEs will be reported promptly to GSK within the timeframes described in Table A, once the investigator determines that the event meets the protocol definition of a SAE.

Table B. Timeframes for submitting serious adverse event and other events reports to GSK Biologicals

| Type of Event              | Initial Reports |  | Follow-up of Relevant Information on a Previous Report |  |
|----------------------------|-----------------|--|--|--|
|                            | Timeframe       | Documents                                  | Timeframe  | Documents                                  |
| SAEs                       | 72 hours*‡      | electronic Expedited Adverse Events Report | 72 hours***  | electronic Expedited Adverse Events Report |
| AEs of specific interest** | 72 hours*‡      | electronic Expedited Adverse Events Report | 72 hours***  | electronic Expedited Adverse Events Report |

\* Timeframe allowed after receipt or awareness of the information.

\*\* AEs of specific interest include meningitis and pIMDs.

\*\*\* Within receipt of information on the outcome of the SAE

‡ The investigator will be required to confirm review of the SAE/AEs of specific interest causality by ticking the 'reviewed' box in the GSK electronic Expedited Adverse Events Report within 72 hours of submission of the SAE/AEs of specific interest.

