#### Reporting events of special interest

AEs of specific interest (pIMDs, and meningitis occurring within 30 or 42 days of vaccination) will be reported promptly to GSK within the timeframes described in Table B, once the investigator determines that the event meets the protocol definition of an AEs of specific interest (pIMDs and meningitis within 30 or 42 days of vaccination).

Contact information for reporting serious adverse events and AEs of specific interest

| Study Contact for Reporting SAEs and AEs of specific interest*  |
|--|
| Refer to the local study contact information document.   |
| Back-up Study Contact for Reporting SAEs and AEs of specific interest*  |
| 24/24 hour and 7/7 day availability:   |
| GSK Biologicals Clinical Safety & Pharmacovigilance
Outside US & Canada sites:
[contact] or [contact]
Email address: [contact] |

## Appendix 3

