### **Pre-specified Secondary analyses**

#### **Safety signals from the RTS,S/AS01 phase 3 studies**

The incidence of meningitis has been very low in the study cohort, with no events in the first three years of the trial. A 95% confidence interval for the incidence rate of meningitis among children vaccinated with RTS,S/AS01, over the whole intervention period, up to the age of five years, will be calculated.

The incidence of cerebral malaria among children vaccinated with RTS,S/AS01E will be investigated by comparing the RTS,S/AS01 groups with the SMC alone group, controlling for SMC status using an indicator variable. Cox regression will be used to obtain the hazard ratio and its 95% confidence interval over the whole intervention period, up to the age of five years.

The incidence of febrile convulsions not related to malaria or another obvious cause among children vaccinated with RTS,S/AS01 will be investigated as for cerebral malaria, i.e. by comparing the RTS,S groups with the SMC alone group, controlling for SMC status using an indicator variable. Cox regression will be used to obtain the hazard ratio and its 95% confidence interval over the whole intervention period, up to the age of five years. The excess cases per 1000 child-years at risk, based on the incidence rate differences will also be presented. The subset of febrile convulsions that occurred within 7 days of vaccination will also be analysed.

An exploratory analysis for data from the first three years of the trial found no evidence that RTS,S/AS01 increases mortality in girls. This will be repeated over the whole intervention period, up to the age of five years.

This was done by comparing the incidence of deaths using Cox regression, with an interaction between a dummy variable indicating receipt of RTS,S/AS01E and gender. The Wald test p-value for the interaction term will be used to assess evidence for effect modification. This model will also include a dummy variable for SMC to adjust for SMC receipt. This will enable the

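### The SAP has no by-arm analysis of potential immune-mediated disease or of all seizures within 30 days, though the protocol makes both adverse events of special interest; cases not admitted to hospital go uncompared.

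*Combined protocol and SAP*

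**What the plan says.** The protocol defines the events of special interest in Appendix 2, A.2: "AEs of specific interest for safety monitoring include all seizures occurring within 30 days post-vaccination, meningitis and pIMDs and will be recorded in the CRF". Its Table A lists the pIMDs. Section 2.4.1 adds that "both meningitis and pIMDs will be monitored as AEs of specific interest for the duration of the study".

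Two later places in Appendix 2 differ. The footnote to Table B (section D) reads "AEs of specific interest include meningitis and pIMDs", with no mention of seizures. The paragraph on reporting events of special interest says "AEs of specific interest (pIMDs, and meningitis occurring within 30 or 42 days of vaccination) will be reported promptly to GSK".

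The SAP's section on safety signals from the phase 3 studies covers four things:
- meningitis, through "A 95% confidence interval for the incidence rate of meningitis among children vaccinated with RTS,S/AS01";
- cerebral malaria, by Cox regression;
- febrile convulsions, by Cox regression and rate difference over the whole intervention period: "The incidence of febrile convulsions not related to malaria or another obvious cause among children vaccinated with RTS,S/AS01 will be investigated". A further sentence adds "The subset of febrile convulsions that occurred within 7 days of vaccination will also be analysed";
- mortality by sex.

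Elsewhere, the SAP's Serious Adverse Events section tabulates hospitalisations and deaths by group and cause. The multiplicity section promises p-values and confidence intervals for safety outcomes without listing them.

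**The concern.** The protocol singles out three kinds of event for special attention, and the SAP carries them through unevenly. pIMDs appear in no endpoint, analysis or dummy table. Seizures are analysed only if febrile and without an obvious other cause, and the only post-vaccination window is 7 days.

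This matters because protocol section 8.1 states that there is no previous experience of sixth and seventh RTS,S/AS01 doses. Section 2.3.3 makes any continuation of seasonal vaccination to age 10 conditional on repeated boosters being shown to be safe. A safety conclusion from this trial would be expected to state, by arm, what was seen of each event declared in advance to be of special interest.

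The cause-based exclusion adds a difficulty. Whether a convulsion is attributed to malaria depends partly on whether the child has malaria, and the interventions change that. The SAP's superiority paragraph reports incidence about 60% lower in the combined group during the first three years. Similar seizures could therefore be classified differently by arm. A count of all seizures, whatever the cause, avoids that dependence.

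**Working it through.** The plan states no sample size or figure for these events, so there is nothing to reproduce. The check compares texts and then illustrates size.

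**Where each kind of event would be seen by arm under the SAP**

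| Event | By-arm analysis in the SAP |
|---|---|
| pIMD, admitted or fatal | SAE table by cause (descriptive); also counted within all-cause admissions or deaths |
| pIMD, not admitted (Table A includes vitiligo, alopecia areata and Bell's palsy, which need not lead to admission) | None |
| pIMDs as a defined group, with an interval | None |
| Febrile convulsion with no malaria or other obvious cause, days 0–7 | Whole-period Cox model and 7-day subset |
| The same, days 8–30 | Whole-period Cox model, not shown separately |
| Seizure that is afebrile or attributed to malaria or another cause, admitted | SAE table by cause; cerebral malaria also has its own Cox model |
| The same, not admitted | None |

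The SAP defines an SAE as hospitalisation or death. Protocol Appendix 2 also counts life-threatening events and disability or incapacity. A disabling pIMD managed without admission would therefore be an SAE under the protocol but outside the SAP's table.

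The SAP does not say whether the 7-day subset keeps the cause exclusion. The subset spans 7/30 = 23% of the protocol's seizure window.

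**What a by-arm pIMD table could report**

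Inputs: protocol section 10.2 plans 20,625 child-years in all, or 20,625/3 = 6,875 per group. The two RTS,S groups together have 2 × 6,875 = 13,750. For k events in T child-years, the exact two-sided 95% upper limit is χ²(0.975; 2(k+1)) / (2T).

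- k = 0: 3.689/13,750 = 0.27 per 1000 child-years
- k = 1: 0.41 per 1000
- k = 3: 0.64 per 1000

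For the extension, both documents give 1,367 child-years per group in year 4, so 2,734 in the RTS,S groups. Zero events would give 3.689/2,734 = 1.35 per 1000 child-years. The documents give no person-time for year 5; adding it would lower this limit.

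**Why counts and intervals rather than a hazard ratio**

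Protocol section 2.4.1 reports five febrile convulsions in the first three years, arm not known. With two of three children allocated to RTS,S, and assuming equal risk and equal follow-up in every group, the chance that all n events fall in the RTS,S groups is (2/3)^n. For n = 5 this is 0.13. For n = 9 it is 0.026, and for n = 10 it is 0.017. At least 10 events, all in RTS,S recipients, would be needed to reach a one-sided 0.025.

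**The case against.** The strongest defence is that no promised endpoint has been dropped. The protocol's secondary safety endpoint (section 4.2.2e) names the immediate response to vaccination and SAEs, with special reference to meningitis and cerebral malaria. It names neither pIMDs nor seizures. Events of special interest have their own route, expedited reporting to the manufacturer. Section 2.4.1 treats pIMD as a theoretical concern. Setting aside convulsions due to malaria is a reasonable way to isolate reactogenicity. All of this stands, and it limits the severity.

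A reader might infer that pIMDs are lost altogether. The documents do not support that: an admitted or fatal pIMD belongs in the SAE table by group and cause, as does an admitted seizure of any type.

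A reader might also infer that convulsions from day 8 to day 30 are discarded. They are not: eligible ones enter the whole-period Cox model, and the 7-day analysis is an addition to it. What is missing is a separate 30-day display and the seizures that the eligibility wording excludes.

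Nor should the 30-day all-seizure definition be treated as settled, because the Table B footnote and the reporting paragraph in Appendix 2 give a different list.

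Ascertainment is the last limit. Daily visits cover about 150 children per country for seven days (section 8.1), clinic surveillance is directed at malaria (section 7.6.1), and safety case-finding is hospital-based. No active search for non-admitted pIMDs is described, so a zero count could partly reflect under-detection.

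**Conclusion.** The gap is real but limited. The protocol requires pIMDs and all seizures within 30 days to be recorded as events of special interest; the SAP plans no analysis of either as defined. What escapes every by-arm analysis is the non-admitted part: pIMDs without admission, and non-admitted seizures that are afebrile or attributed to malaria or another cause. A named pIMD grouping with an interval estimate is also missing.

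Severity is minor to moderate. It affects what the trial can state about the safety of doses six and seven, and leaves the primary efficacy result untouched. The 0.27 per 1000 child-years is an illustration. It assumes the planned 13,750 RTS,S child-years, no events and complete detection; with incomplete detection it is a limit on the rate of detected events only.

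**What to change.** Add two by-arm tables to the SAP's safety-signals section, each with counts, rates and exact 95% confidence intervals, before the randomisation code is released:

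1. pIMDs as listed in protocol Table A, whether admitted or not, over the whole follow-up and over the extension alone.
2. All seizures of any cause within 30 days of each dose. Keep the planned febrile-convulsion and 7-day analyses as subsets, and state whether the 7-day subset keeps the cause exclusion.

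No hazard ratio is needed. Note beside the first table how non-admitted pIMDs came to be detected.

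Reconcile Appendix 2, A.2 with the Table B footnote and the reporting paragraph, which omit seizures and give 30 or 42 days, and with section 2.4.1, which says the duration of the study. The tables should then follow the reconciled definition.

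The cost is two tables from data that the protocol says are recorded in the CRF. The downside is small counts, wide intervals and possible under-ascertainment of events that did not lead to admission.

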### **2.3.2 Progress with the trial**

In Burkina Faso, 92% of enrolled children received all three priming doses of RTS,S/AS01E or control (rabies) vaccine in 2017, 90% received their first booster dose in June 2018 and 90% received their second booster dose in June 2019. In Mali, 93% of children received all three priming doses of RTS,S/AS01E or comparator vaccine in 2017, 88% received their first booster dose of vaccine in June 2018 and 85% their second booster dose of vaccine in June 2019. Coverage with SMC or placebo has been high throughout the trial with nearly 90% of children receiving all four monthly SMC courses during the first and second years of the study. Retention of children in the trial has also been high. At a census undertaken early in 2019, 2547 (92%) of the 2777 children enrolled in Burkina Faso and 2816 (90%) of the 3143 children initially enrolled in Mali were still contributing to the study.

The investigators remain blind to the randomisation code. However, in March 2019 members of the trial's Data and Safety Monitoring Board (DSMB) met to review safety outcomes during the first two years of the trial. They reviewed data on deaths, deaths attributed to malaria, hospital admissions and hospital admissions attributed to malaria broken down by study group. The board concluded that it was safe for the trial to continue for a third year retaining the three initial study groups. This recommendation implies that during 2018 a single booster dose of RTS,S/AS01E was not markedly inferior to SMC in protecting against the outcomes considered by the board and provided encouragement for continuation of the trial into a third year and, potentially, for longer.

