### **Serious Adverse Events**

In addition to the comparison of incidence rates described above, serious adverse events (SAEs) defined as hospitalisations or death, occurring at any time during the study will be tabulated by study group according to their cause.

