## Statistical methods

### Reference group

As SMC is the current standard of care, the SMC alone group will be considered as the reference group for comparisons with RTS,S/AS01E alone, and the combined group. Comparisons will also be made between the RTS,S/AS01E alone and the combined group.

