### **Secondary endpoints**

Secondary outcomes which are passively detected events, will be analysed in a similar way as for the primary outcome, i.e. estimating the hazard ratio using Cox regression with a robust standard error.

The prevalence ratio of secondary endpoints measured at the weekly survey (aggregated into three-month periods), and at end of season surveys (including *P. falciparum* parasitaemia, anaemia, etc) will be estimated using Poisson regression, with a robust standard error for the individual, as described in Zou, 2004 (10).

Linear regression models will be used to compare mean haemoglobin concentration between the groups.

Arithmetic mean parasite densities (including in the calculation samples which are parasite negatives, as having density of zero), will be compared between arms using Poisson regression with a robust standard error.

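### With SMC coded by allocation, the SMC-adjusted hazard ratio for febrile convulsions and cerebral malaria is Combined vs SMC alone, not the stated comparison of both RTS,S groups with SMC alone

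*Combined protocol and SAP*

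**What the plan says.** The SAP section on safety signals from the RTS,S/AS01 phase 3 studies sets out two Cox analyses over the whole intervention period. Cerebral malaria "will be investigated by comparing the RTS,S/AS01 groups with the SMC alone group, controlling for SMC status using an indicator variable". Febrile convulsions without malaria or another obvious cause follow the same approach, "i.e. by comparing the RTS,S groups with the SMC alone group, controlling for SMC status using an indicator variable". Each is to yield a hazard ratio with a 95% confidence interval. For febrile convulsions the section adds excess cases from incidence rate differences, without naming the arms contrasted. It also states that "The subset of febrile convulsions that occurred within 7 days of vaccination will also be analysed", without naming a model.

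Three other SAP sections bear on the point:

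- Reference group: "the SMC alone group will be considered as the reference group for comparisons with" each of the other two arms, and RTS,S alone is also compared with Combined.
- Secondary endpoints: "Secondary outcomes which are passively detected events, will be analysed in a similar way as for the primary outcome".
- Serious Adverse Events: these events, "defined as hospitalisations or death, occurring at any time during the study will be tabulated by study group according to their cause".

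**The concern.** The wording promises a comparison of vaccinated children, in both RTS,S arms, with the SMC-alone arm. A reader of the trial report would take the hazard ratio to describe all RTS,S recipients. But the only arm without SMC is RTS,S alone, so an allocation-coded SMC indicator simply marks that arm. Once the indicator is in the model, the RTS,S-alone children determine the SMC term and no longer inform the RTS,S term.

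What is at stake is the meaning of two safety estimates. Half of the vaccinated arms would not inform the reported vaccine hazard ratio, and an imbalance seen only in RTS,S alone would not appear in it.

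**Working it through.** The documents give no event count, power or precision for these two models, so there is no planned figure to reproduce.

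**Inputs.** The three arms are in the SAP under Study groups. Stratification by country only is in the SAP under Covariates. The model is read as one RTS,S indicator plus one SMC indicator without interaction. Separate indicators for the two RTS,S arms plus an SMC indicator would be collinear.

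**Step 1: coding by allocation.** Let R mark RTS,S and S mark SMC. Let Q mark the RTS,S-alone arm and C the Combined arm.

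| Arm | R | S | Q | C |
|---|---|---|---|---|
| SMC alone | 0 | 1 | 0 | 0 |
| RTS,S alone | 1 | 0 | 1 | 0 |
| Combined | 1 | 1 | 0 | 1 |

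Hence R = Q + C and S = 1 − Q.

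**Step 2: algebra.** bR·R + bS·S = bR(Q + C) + bS(1 − Q) = bS + (bR − bS)·Q + bR·C. The constant bS is absorbed into the baseline hazard of each country stratum. So exp(bR) is the Combined vs SMC alone hazard ratio, and exp(bR − bS) is RTS,S alone vs SMC alone. Equivalently, inverting the matrix [1, R, S] (rank 3) gives bR weights of −1 on SMC alone, 0 on RTS,S alone and +1 on Combined.

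**Step 3: numerical check.** Four simulated data sets were fitted with country-stratified Cox models and Efron ties. Each had 1,965 children per arm and 3.5 years of follow-up. The true rates per 1000 child-years are assumptions. Arms are listed as SMC alone / RTS,S alone / Combined.

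| Assumed rates | Events | RTS,S HR, SMC-adjusted | Three-group Combined vs SMC alone | Three-group RTS,S alone vs SMC alone | RTS,S-alone arm dropped | Both RTS,S arms pooled, unadjusted |
|---|---|---|---|---|---|---|
| 2 / 2 / 2 | 13 / 14 / 13 | 1.0055 | 1.0055 | 1.0792 | 1.0079 | 1.0425 |
| 2 / 10 / 2 | 16 / 80 / 9 | 0.5597 | 0.5597 | 5.0779 | 0.5530 | 2.7965 |
| 2 / 2 / 10 | 13 / 15 / 53 | 4.1238 | 4.1238 | 1.1528 | 4.1200 | 2.6289 |
| 5 / 10 / 5 | 33 / 76 / 29 | 0.8766 | 0.8766 | 2.3117 | 0.8773 | 1.5915 |

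The adjusted estimate equals the three-group Combined estimate to four decimals, and so do the standard errors. Dropping the RTS,S-alone arm changes it by about 1% at most, because that arm then matters only through the shared baseline risk sets. The crude counts in the second row agree: 9/16 = 0.56 for Combined and 80/16 = 5.0 for RTS,S alone. The standard error of the adjusted log hazard ratio is √(1/16 + 1/9) = 0.417, with no contribution from the 80 RTS,S-alone events.

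**Step 4: what the estimate can and cannot show.**

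- Excess shared by both RTS,S arms, ratio θ: exp(bR) = θ, so it is seen.
- Three-fold excess in RTS,S alone only: bR = −0 + 0·log 3 + 0 = 0, so the reported hazard ratio is 1.00. A three-level factor returns 3.00 for RTS,S alone and 1.00 for Combined.

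**Step 5: rate difference.** If the same two indicators are used on the additive scale, the RTS,S term is the Combined rate minus the SMC-alone rate. With the assumed rates 2, 10 and 2 per 1000 that is 2 − 2 = 0, while RTS,S alone vs SMC alone is 10 − 2 = 8 per 1000 child-years.

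**Step 6: other cover for the two outcomes.** Cerebral malaria is named under SAP endpoint 2.2.3. The Secondary endpoints method and the Reference group rule therefore give its hazard ratio by arm. Febrile convulsions are not among the endpoints listed in 2.1 to 2.5, to which that method applies. The serious-adverse-event table would show hospitalised or fatal cases by arm, but as counts without an effect estimate.

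**The case against.** The strongest reply is that the model is right and only its label is loose. With no arm receiving neither intervention, controlling for SMC can only mean a vaccine effect at fixed SMC, and the SAP states the adjustment in the same sentence as the comparison. That stands: the estimate is a proper randomised contrast.

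Second, both RTS,S arms receive the same vaccine on the same schedule, so a harm confined to RTS,S alone is a constructed case. For cerebral malaria such a pattern could simply be the lack of SMC, which the indicator is there to remove. That also stands, and it limits the consequence. It does not make the wording match the contrast.

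Third, the Reference group rule is not restricted by endpoint and might be taken to cover febrile convulsions. It names a reference group but does not plan a model for an outcome whose own paragraph specifies a different one.

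Three stronger readings are tempting and are not supported:

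- A reader might infer that the safety analysis would miss a vaccine harm. It would not miss one common to both RTS,S arms.
- A reader might infer that the result hangs on an unstable definition of SMC status, since the mortality model says "This model will also include a dummy variable for SMC to adjust for SMC receipt". The SAP puts all secondary outcomes on modified intention to treat, which favours allocation, and nothing in the section suggests a time-varying term. The undefined covariate is a missing detail, not evidence of divergent results.
- A reader might infer that the two RTS,S arms should be pooled without adjustment. Over the whole period that would mix the vaccine effect with the absence of SMC.

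**Conclusion.** The point holds as a mismatch between the stated comparison and the contrast the model returns. Under allocation coding, with one indicator per intervention, the RTS,S hazard ratio is Combined vs SMC alone and gives zero weight to RTS,S alone. The identity is algebraic and does not depend on event rates or on stratification by country. The rates and the three-fold excess used above are illustrations, not expectations.

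For cerebral malaria it is mainly a labelling error. For febrile convulsions it leaves RTS,S alone vs SMC alone without an explicitly planned hazard ratio. Events are few: protocol section 7.2 reports five febrile convulsions in the first three years, and section 2.4.1 says it is not known whether all of those children had received RTS,S. That count is not stated to follow the SAP's narrower definition. Severity is minor, and no primary conclusion is affected.

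**What to change.** For both outcomes, replace the two indicators with a three-level group factor, SMC alone as reference and stratified by country. Report:

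- Combined vs SMC alone, under that name and described as the vaccine effect given SMC. It is the same number the planned model would produce under allocation coding.
- RTS,S alone vs SMC alone, with a note that it also reflects the absence of SMC and cannot separate the two.

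Name the same two contrasts for the febrile-convulsion rate difference. With a group factor, the meaning of SMC status no longer needs defining for these outcomes.

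The cost is a few sentences in the SAP and one model line per outcome, on data already collected. The downside is one more estimate per outcome from very few events, so the intervals will be wide and should be presented as such.
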